**Ectopy Triggering Ganglionated Plexus Ablation to Prevent
Atrial Fibrillation (GANGLIA-AF)**

ClinicalTrials.gov ID: NCT02487654

Document date: 13th December 2021

STUDY PROTOCOL

GANGLIA-AF (ClinicalTrials.gov identifier NCT02487654) was a prospective, multicenter, randomized, single-blinded clinical study recruiting patients with paroxysmal AF indicated clinically for AF ablation. The recruitment period was between May 2017 and May 2019. Three UK centers participated in the study: Hammersmith Hospital, Imperial College Healthcare NHS Trust, UK; Derriford Hospital, University Hospitals Plymouth NHS Trust, UK; St Bartholomew's Hospital, Barts Health NHS Trust, UK. All patients gave written informed consent, and the study was approved by the local research ethics committee. Patients with symptomatic drug-refractory paroxysmal AF indicated for ablation were recruited to the study. The inclusion and exclusion criteria are included on the ClinicalTrials.gov PRS.

Patients were randomized to PVI or to GPA without PVI. Randomization was performed using a permuted block “sealed envelope” approach. The first block of randomization was performed on 21 consecutive patients, randomized 2:1 to GPA (GPA, n = 14; PVI, n = 7). This was in anticipation for a high rate of crossover from the GPA group as experienced in our previous pilot study.

Afterward, randomization was switched to 1:1 in blocks of 10 for the remainder of the recruitment. Patients and their cardiologists providing their usual care were blinded to their randomization. Operators on the day of ablation, the data collector, and the analyst were unblinded to randomization.

Protocol for all patients

Preoperative work-up

All patients discontinued AADs and β -blockers 5 half-lives before the procedure. Amiodarone was discontinued at least 2 months before the procedure. All patients provided written informed consent for participation in the study, which was approved by the health research authority and the local research ethics committee. Complete blood count, urea and electrolytes, C-reactive protein were measured on the morning before the procedure to ensure suitability for ablation.

Clinical procedures

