In this study, for our synchronized HFS protocol, the left atrium was paced at high output (10 V) from the ablation catheter during sinus rhythm (SR) to check for atrial capture and to exclude ventricular capture. Then, we delivered short bursts of HFS trains (10 V, 80 ms duration, 40 Hz) coupled to each paced stimulus to ensure that HFS was delivered within the local atrial refractory period. This stimulated only the nerves and avoided direct myocardial capture. We delivered up to 15 trains of synchronized HFS per test site. If atrial ectopy or AF was triggered, we discontinued pacing and HFS immediately to avoid direct myocardial capture and sustained AF.

Continuous HFS was performed during AF by delivering HFS (10 V, 20 Hz) continuously for up to 10 seconds or until asystole occurred.

The definition for a *positive ET-GP* was reproducible induction of PV or atrial ectopy, AF, or atrial tachycardia (AT). Reproducibility was assessed up to 3 times with HFS. The definition for a *positive AVD-GP* was $\geq 50\%$ increase in the R-R interval during HFS compared with the average 10 R-R intervals before HFS.

The main goal of our study was to map ET-GPs with synchronized HFS during SR. However, if patients developed sustained AF during GP mapping, GPs were ablated until successful restoration of SR. A positive response to GPA during sustained AF was termed “acute AF modulation,” and this was defined as follows: (1) termination to SR, (2) organization to AT, and (3) slowing of AF cycle length by ≥ 30 ms. A subgroup analysis was performed in patients who underwent GPA to correlate long-term freedom from ≥ 30 seconds of AF/AT recurrence. Patients who underwent GPA were divided into those who had (1) $<100\%$ success in acute AF modulation, (2) 100% success in acute AF modulation, and (3) no sustained AF with GP stimulation.

If all GPs were ablated and the patient was still in AF, up to 3 direct current cardioversions were performed to restore SR and to complete GP mapping. If patients remained in incessant AF, AVD-GPs were mapped with continuous HFS and ablated. We targeted AVD-GPs as well in this instance because significant overlap exists with ET-GPs and we wanted to target as many ET-GPs as possible.

¹⁰

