After completing GP mapping, all GPs were ablated by delivering a cluster of 3 point-by-point lesions around each GP site, with the contact force of >3 g. Each ablation lesion was for 30 seconds at 30 W except in the posterior wall, where it was limited to 25 W. Catheter irrigation was set to 17 mL/min. This was usually adequate to render any GP negative for any response with repeat HFS testing. All ablated GPs were retested with HFS after ablation. If there was still a positive response, further ablation was performed until no further positive responses could be evoked.

PVI

For patients randomized to the PVI arm, wide antral circumferential ablation was performed around the PVs by using contiguous point-by-point radiofrequency (RF) ablation lesions. The

entry and exit blocks of PVs were confirmed using a PV catheter. Operators used the ablation index to guide PVI on >60% of patients who completed PVI.

Clinical follow-up

Patients were followed up and monitored for 12 months, with continuous remote contact with a clinician. Patients were fitted with 48-hour Holter monitors at 3-, 6-, 9-, 12-month intervals. If patients experienced symptoms between these 3-monthly time points, they were offered further Holter monitors in an attempt to record their symptomatic arrhythmia. Patients with pacemakers, loop recorder devices, and personal AliveCor Kardia electrocardiogram (ECG) (AliveCor Inc, Mountain View, CA) monitoring devices were interrogated throughout their follow-up. Any significant arrhythmia identified on their interrogation counted toward the primary end point regardless of the Holter results. We encouraged patients to discontinue all antiarrhythmic drugs (AADs) following the 3-month blanking period after their ablation procedures, but this was not mandated in the protocol.

Repeat AF ablation

Patients who were randomized to GPA returning for redo AF ablation procedures had repeat HFS testing. This identified any recurrence of GPs or new GPs not previously identified. All GPs identified in the redo procedure were ablated in addition to PVI. Patients who were randomized to PVI returning for redo AF ablation procedures had repeat PVI only.

End point definition

The primary end point was any documented atrial arrhythmia (AF, AT, or atrial flutter) lasting for ≥ 30 seconds consecutively recorded on the Holter monitor, 12-lead ECG, pacemaker, loop recorder, and AliveCor Kardia recorded ECG after a 90-day blanking period.

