The secondary end points included repeat ablation for AF/AT/atrial flutter after a 90-day blanking period, mortality, and any significant complications related to the procedure (bleeding, thrombosis, phrenic nerve palsy, and cardiac tamponade) requiring intervention.

Statistics

Data analyses were conducted using the per-protocol (PP) study population. The PP study population excluded patients who were withdrawn after randomization. For sample size calculation, it was estimated that at a statistical power of 80% at a 5% significance level, 108 patients were required to detect 25% difference in primary end point, where 45% in PVI and 20% in GPA are predicted to have recurrent AF/AT. We enrolled 116 patients to allow for ~5% not completing follow-up.

Statistical analysis was performed using SPSS Version 28 (IBM Corporation, Armonk, NY) and Prism 5 (GraphPad, San Diego, CA). Continuous variables were expressed as mean \pm SD. Categorical variables were expressed as number and percentage. D'Agostino and Pearson omnibus and Shapiro-Wilk tests were performed to assess the normality of continuous variables before the comparison of means tests. Mann-Whitney *U* test, Fisher exact test, and unpaired *t* test were used for comparison of means. An event-free survival was estimated using a Kaplan-Meier curve for the primary end point. Clinical parameters associated with AF recurrence and other procedural parameters were studied using univariate and stepwise multivariate analysis in a Cox regression model. All variables with *P* values $\leq .05$ from the univariate analysis and well-established risk factors for AF recurrence, such as age and hypertension, were entered into the multivariate regression analysis. A *P* value of $<.05$ indicated statistical significance.

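### The complication end point counts events only if they required intervention and leaves open whether its four-item list is closed, so non-fatal procedural harm can go uncounted

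*Combined protocol and SAP*

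**What the plan says.** The End point definition section names three kinds of secondary end point. Two are given in the words "The secondary end points included repeat ablation for AF/AT/atrial flutter after a 90-day blanking period, mortality". The third is "any significant complications related to the procedure (bleeding, thrombosis, phrenic nerve palsy, and cardiac tamponade) requiring intervention".

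Repeat ablation reflects recurrence, so mortality and the complication item are the only stated safety measures. The protocol and SAP describe no wider adverse-event collection, severity grading, time window for complications or independent adjudication. They do not define what makes a complication significant or what counts as an intervention.

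On blinding, the opening Study Protocol section says: "Operators on the day of ablation, the data collector, and the analyst were unblinded to randomization". The sentence before it says that patients and the cardiologists giving their usual care were blinded.

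**The concern.** An event must pass several conditions to be scored. It must be significant, related to the procedure, and severe enough to have required intervention. On the narrower reading it must also be one of four types. The intervention condition makes the count depend on how an event was managed as well as on whether it happened. A phrenic nerve palsy watched until it recovers is harm to the patient, but it is recorded as no complication.

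What is at stake is the safety comparison between an experimental strategy (GPA without PVI) and the established one. If the report says that complications did not differ, the reader needs to know whether few events occurred or few met the definition. As written, the end point cannot separate these two explanations for non-fatal events.

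**Working it through.** **The plan's own figure.** The only related number in the plan is the sample size, which is for the primary end point: "at a statistical power of 80% at a 5% significance level, 108 patients were required", with "45% in PVI and 20% in GPA are predicted to have recurrent AF/AT". Take the two-proportion formula with pooled variance, two-sided 5%, no continuity correction, and mean rate (0.45 + 0.20)/2 = 0.325:

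n = [1.960 × √(2 × 0.325 × 0.675) + 0.842 × √(0.45 × 0.55 + 0.20 × 0.80)]² / 0.25² = 53.9, so 54 per arm and 108 in total.

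This reproduces the plan. No complication rate enters the formula, so any change to the complication definition leaves 108 (and the 116 enrolled) as they are.

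**The intervention condition.** It needs no interpretation. It sits at the end of the definition and applies to everything before it, so a listed event without intervention is not scored.

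**The list.** Three places bear on whether it is closed.

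- The four types stand in brackets with no wording that marks them as examples.
- The Statistics section does mark an open list when it means one: "well-established risk factors for AF recurrence, such as age and hypertension".
- The primary end point uses brackets to define: "any documented atrial arrhythmia (AF, AT, or atrial flutter) lasting for ≥ 30 seconds".

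These make a closed list the more natural reading. Against that, the definition begins with any significant complications, which the four types could merely illustrate. The documents do not settle it.

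**What each reading does.**

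| Event | List closed | List illustrative |
|---|---|---|
| Listed event, observed only | Not counted | Not counted |
| Stroke or TIA, no intervention | Not counted | Not counted |
| Stroke or TIA, with intervention | Only if classed as thrombosis | Counted if judged significant |
| Effusion without tamponade, oesophageal injury, pulmonary vein stenosis or persistent conduction disturbance, with intervention | Not counted, unless it is also a listed type | Counted if judged significant |
| The same events, no intervention | Not counted | Not counted |

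The under-count of events without intervention is the same on both readings. Only the treatment of unlisted types differs.

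**Illustration of size.** The rates below are assumptions, not figures from the documents. Take 58 per arm (116/2), a true rate of any complication of 4% or 10%, and a share s of these that meets the definition. The expected number counted is 58 × rate × s. The chance that an arm shows none is (1 − rate × s)^58.

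| True rate | Occurring per arm | s | Counted per arm | Chance of zero counted |
|---|---|---|---|---|
| 4% | 2.32 | 25% | 0.58 | 56% |
| 4% | 2.32 | 75% | 1.74 | 17% |
| 4% | 2.32 | 100% | 2.32 | 9% |
| 10% | 5.80 | 25% | 1.45 | 23% |
| 10% | 5.80 | 75% | 4.35 | 1% |
| 10% | 5.80 | 100% | 5.80 | 0.2% |

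An equal split is a simplification. The first 21 patients were allocated 14 to GPA and 7 to PVI, which leaves 116 − 21 = 95 at 1:1. The arms are then about 14 + 47.5 = 61.5 and 7 + 47.5 = 54.5. In the first row, 0.99^62 = 54% and 0.99^54 = 58%, so little changes.

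**The case against.** **What stands against the point.** The closed list is a reading, not a stated rule, so it cannot be asserted that only four event types count. Fatal harm of any type is captured under mortality. The documents do not say that other events went unrecorded, only that no other collection is described. An intervention threshold also has a merit: with an unblinded data collector, it is arguably less open to judgement than any adverse event graded by severity. Recruitment ended in May 2019 and the document is dated December 2021, so redefining the end point now would be post hoc. All of this limits the request to clarification and supplementary reporting. None of it removes the intervention condition.

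**Stronger readings that the documents do not support.**

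- A reader might infer that harms specific to GPA are exactly those the definition misses, because "Continuous HFS was performed during AF by delivering HFS (10 V, 20 Hz) continuously for up to 10 seconds or until asystole occurred". But asystole is given there as a point at which stimulation ends, and lengthening of the R-R interval is the defined mapping response. Mapping of AVD-GPs by continuous stimulation is described for patients who remained in AF after cardioversion. The documents give no evidence of a resulting harm, and no direction of bias between arms is established.
- A reader might infer that operators who knew the arm decided relatedness and intervention. The documents do not say who decided either. Usual-care cardiologists were blinded, so later events may have been managed by blinded clinicians.
- A reader might take the upper limit after zero events as the size of the defect. The one-sided 95% limit, 1 − 0.05^(1/n), is 4.7% at n = 62 and 5.4% at n = 54. It depends only on sample size and would be the same for a wider definition.

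**Conclusion.** The point holds in a limited form. The plan's only stated safety measure apart from mortality excludes, by explicit rule, any complication that did not require intervention. It also leaves unclear whether types outside the four named ones count. This is a rule that under-counts non-fatal harm, rather than a detail left out of the text.

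The size is unknown, because the documents give neither a complication rate nor the share needing intervention. Over the assumed ranges (4% to 10% true rate, 25% to 75% meeting the definition, 58 per arm), an arm would show no counted complication with a chance of 56% down to 1%. With full capture the chance would be 9% down to 0.2%. A low or zero count would therefore say little about total procedural harm.

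The conclusion does not rest on the list being closed, on any harm peculiar to GPA, or on who judged the events. It does not touch the primary end point or its power.

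**What to change.** 1. State in the End point definition section whether the four types are the complete list, and define what counts as significant and as requiring intervention.
2. Add a supplementary safety analysis of all procedure- or stimulation-related adverse events found in existing records, by arm, type and severity, whether or not intervention was needed. Name the types to be looked for, including stroke/TIA, effusion without tamponade, oesophageal injury, pulmonary vein stenosis and persistent conduction disturbance. State the denominator, since the Statistics section excludes patients withdrawn after randomization.
3. Keep events requiring intervention as the pre-stated subset, reported alongside, so the planned figure remains available.
4. Use objective event definitions and label the analysis supplementary.

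The cost is a change of wording and a review of existing records, with no extra tests and no change in sample size. How complete those records are is not known from the documents. Reported complication rates will rise in both arms. There is also some risk that events are ascertained differently between arms, because the operators, data collector and analyst knew the allocation. The objective definitions in step 4 are meant to limit that risk.

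### The 80% power figure carries no allowance for crossover from GPA, which the protocol anticipated, and the plan does not say how crossovers are analysed

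*Combined protocol and SAP*

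**What the plan says.** The opening section of the study protocol defines the contrast: "Patients were randomized to PVI or to GPA without PVI". It then describes a first block of 21 patients allocated 2:1 (14 GPA, 7 PVI) and gives the reason: "This was in anticipation for a high rate of crossover from the GPA group as experienced in our previous pilot study". After that block, "randomization was switched to 1:1 in blocks of 10 for the remainder of the recruitment". Crossover is not defined and the pilot rate is not given.

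The Statistics section gives the sample size: "at a statistical power of 80% at a 5% significance level, 108 patients were required to detect 25% difference in primary end point". The assumed recurrence rates behind it are 20% for GPA and 45% for PVI. Enrolment was raised to 116, and the only reason given is about 5% incomplete follow-up. Crossover is not mentioned in that section.

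The analyses use a per-protocol population: "The PP study population excluded patients who were withdrawn after randomization". The section does not say whether a GPA patient who receives PVI counts as withdrawn.

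Under Repeat AF ablation, GPA patients who return for a redo do receive PVI: "All GPs identified in the redo procedure were ablated in addition to PVI".

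**The concern.** The protocol names a threat to the GPA-without-PVI contrast and calls it substantial from its own pilot experience. The power statement has no term for that threat. If GPA patients receive PVI at the index procedure, one of two things happens. If they stay in the GPA arm, the difference between arms is diluted to the extent that they recur more like PVI patients. If they leave the analysis, the GPA arm shrinks, and the loss comes from one arm only, after randomization.

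Two things are at stake. A non-significant result would be read as coming from a trial with 80% power, and nothing in the Statistics section would tell the reader otherwise. And a per-protocol population that may drop GPA crossovers leaves the primary comparison open to bias.

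**Working it through.** **Inputs from the documents.** Recurrence 45% (PVI) and 20% (GPA); power 80%; significance level 5%; 108 required; 116 enrolled; about 5% incomplete follow-up; first 21 patients split 14 GPA and 7 PVI, the remainder 1:1.

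**Assumptions.** The test is two-sided (not stated, but it reproduces 108). Crossover means PVI at the index procedure in a patient randomized to GPA. Its rate c is taken from 5% to 30% of the GPA arm, because no rate is given.

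**1. The plan's own figure.** The pooled two-proportion formula, with mean rate 0.325, is

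n per arm = [1.960 × √(2 × 0.325 × 0.675) + 0.8416 × √(0.45 × 0.55 + 0.20 × 0.80)]² / 0.25²

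= (1.298 + 0.537)² / 0.0625 = 53.9, so 54 per arm and 108 in total.

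The figure is correct for its inputs, and those inputs contain no crossover.

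**2. The rise to 116.** 108 / 0.95 = 113.7, so 114. About 2 patients are spare.

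**3. Patients analysed.** After the first block, 116 − 21 = 95 patients remain, or 47.5 per arm.
- GPA: 14 + 47.5 = 61.5; × 0.95 = 58.4, so 58.
- PVI: 7 + 47.5 = 54.5; × 0.95 = 51.8, so 52.

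**4. Power with crossover.** This is exact power of the uncorrected two-sided chi-square test, summed over all binomial outcomes, with 52 PVI patients at 45%. If crossovers are excluded, the GPA number is 58 less 3, 6, 12 or 17. If they are kept at the PVI rate, the GPA-arm rate is 0.20 + 0.25c. If they are kept at an intermediate 32.5% (an assumption), it is 0.20 + 0.125c.

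| Crossover c | Excluded | Kept, recur at 45% | Kept, recur at 32.5% | Kept, recur at 20% |
|---|---|---|---|---|
| 0% | 82% | 82% | 82% | 82% |
| 5% | 80% | 78% | 80% | 82% |
| 10% | 79% | 73% | 78% | 82% |
| 20% | 77% | 62% | 73% | 82% |
| 30% | 74% | 50% | 67% | 82% |

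**5. What the 2:1 block contributes.** The pooled formula with 116 × 0.95 = 110.2 analysed compares the actual allocation with 1:1 throughout.
- Crossovers excluded: 78.7% v 78.5% at 10% crossover, and 72.5% v 72.0% at 30%.
- Crossovers kept at 45%: 71.1% v 71.0% at 10%.

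The gain is under 1 point.

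**6. If the expectation covers only the first block.** 30% of 14 is about 4 patients. Power is 81% if they are excluded (52 v 54). It is 76% if they are kept at 45% (GPA-arm rate 0.20 + 0.25 × 4/58 = 0.217).

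**7. Dependence on the test.** The only test of proportions that the Statistics section names is the Fisher exact test. Its power for 52 v 58 with no crossover is 78.0%, against 82.0% for the chi-square.

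**The case against.** The strongest reply is that this is a gap in reporting, not a demonstrated loss of power. There are three readings with no loss: the predicted 20% may already include crossovers, crossovers may recur at about 20%, or crossover may mean PVI at a redo, after the primary end point has been counted. The documents exclude none of them. The 2:1 block does suggest that crossovers were expected to deplete the GPA arm, which fits poorly with the first and third readings, but that is inference. This objection stands, and the conclusion is conditional on it.

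A reader might infer that the sample size was miscalculated. It was not: 108 follows from the stated inputs. A reader might also want the crossover rate at which power falls below 80%. No useful cut-off can be given. The margin without crossover is 2 points on the chi-square. The discrete test moves unevenly (79.5% with 2 GPA patients excluded, 80.9% with 4). On the Fisher test, power is already below 80% with no crossover.

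It can also be said that the large losses need 20% to 30% crossover, retention in the GPA arm and recurrence at the full PVI rate. That is true. If crossovers are excluded, the loss is small at 10% to 20%. But exclusion replaces a modest loss of power with a possible bias, and the plan does not say which handling applies.

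Finally, recruitment has closed, and the confidence interval will show the precision achieved. That rules out a change in enrolment. It does not settle the choice of primary population or correct the stated power.

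**Conclusion.** The point holds as an unstated design assumption together with an undefined analysis population. The 80% has no crossover allowance, the 2:1 block does not make up for it, and the rise to 116 is assigned to another purpose.

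Unless one of the three no-loss readings applies, power is below the zero-crossover figure. From 82% (chi-square, 52 v 58), illustrative 10% and 20% crossover rates bring it to about 79% and 77% with exclusion. With retention at the PVI rate they bring it to about 73% and 62%. The omission is certain; its size is not, because the crossover rate, the recurrence rate in crossovers and their handling are all missing.

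The documents do not support a claim that the trial was in fact underpowered by a known amount, or that the plan definitely removes crossovers from the GPA arm.

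**What to change.** 1. In the Statistics section, state that the 80% has no crossover allowance. Define crossover and say whether the predicted 20% includes such patients. Give the power of the enrolled 116 at the pilot crossover rate, using the test actually applied to the primary end point. If the pilot rate cannot be given, report power over a stated range such as 5% to 30%.

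2. Make the primary comparison as randomized, with GPA patients who cross over kept in the GPA arm. Present the per-protocol result that excludes them as a sensitivity analysis, because removing patients from one arm after randomization can bias the comparison.

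The cost is a few sentences and one further analysis of data already collected, with no added patients or visits. The downsides are a less favourable stated power and some dilution of the effect. If crossovers recur at 45%, the as-randomized analysis has 73% power against 79% with exclusion at 10% crossover, and 62% against 77% at 20%. If they recur at 20%, it keeps the full 82%.
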